2. STUDY OBJECTIVES

2.1. Primary objective:

- To evaluate the safety and efficacy of adding CD24Fc to COVID-19 best available treatment by comparing COVID-19 disease status improvement time between CD24Fc and placebo arms within 28 days.

2.2. Secondary objectives:

- Secondary objectives are to compare, for each treatment arm, proportion of patients who died or had respiratory failure (defined as the need for mechanical ventilation, ECMO, non-invasive ventilation, or high flow oxygen devices), the time to disease progression, rate of all-cause death, proportion of death or respiratory failure, rates of hospital discharge time, rate of duration of mechanical ventilation, duration of mechanical ventilation, use of pressors, rate of duration of extracorporeal membrane oxygenation, rate of duration of supplemental oxygen, the length of hospital stay, and the changes in absolute lymphocyte count and markers of inflammation.

2.3. Exploratory objectives:

- To explore the effect of CD24Fc treatment of COVID-19 on systemic steroid dosage, inflammatory cytokine changes, D-dimer level changes, lymphocyte subtype distribution and T lymphocyte activation and exhaustion markers.
- To explore the effect of CD24Fc in pulmonary function, inflammatory markers, cardiac function, liver enzymes and renal function.

2.4. Primary Endpoints:

- Time to improvement in clinical status: the time (days) required for improvement from scale 2 - 4 to scale ≥ 5 or above that is sustained without a drop to below 5 based on NIAID ordinal scales ([Appendix A](#)) within 28 days from randomization.

2.5. Secondary Endpoints:

- Proportion of patients who died or had respiratory failure, defined as the need for mechanical ventilation, ECMO, non-invasive ventilation, or high flow oxygen devices, at Day 29
- Time to disease progression in clinical status: the time (days) for progression from scale 3 or 4 to scale 1 or 2 based on the NIAID ordinal scale within 28 days from randomization.
- All cause mortality at Day 15 and Day 29
- Proportion of clinical relapse, as defined by rate of return to oxygen support for more than 1 day within 28 days from randomization after initial recovery

- Conversion rate of clinical status on Day 8 (proportion of subjects who changed from “scale 2, 3 or 4” to “scale 5 or higher” in the NIAID ordinal scale)
- Conversion rate of clinical status on Day 15 (proportion of subjects who changed from “scale 2, 3 or 4” to “scale 5 or higher” in the NIAID ordinal scale)
- The discharge from hospital time
- Duration of mechanical ventilation (IMV, NIV) (days)
- Duration of pressors (days)
- Duration of extracorporeal membrane oxygenation (days)
- Duration of oxygen therapy (oxygen inhalation by nasal cannula or mask) (days)
- Length of hospital stay (days)
- Absolute lymphocyte count
- D-dimer concentration in the plasma

2.6. **Exploratory endpoints**

- Effect of CD24Fc on systemic steroid usage.
- Effect of CD24Fc on cytokine levels.
- Effect of CD24Fc on lymphocyte subtype distribution.

2.7. **Safety evaluation**

- Adverse events, vital signs, physical examination, laboratory tests (blood routine, blood biochemistry, coagulation function, urine routine), ECG.

3. STUDY DESIGN

3.1. Study Design Overview

This is a Phase III randomized double-blind placebo controlled multi-site study to compare two COVID-19 treatment regimens in hospitalized adult subjects who are diagnosed with severe COVID-19.

Arm A: CD24Fc/Best Available Treatment;

Arm B: placebo/Best Available Treatment.

CD24Fc will be administered as single dose of 480mg via IV infusion on Day 1. Total of 270 subjects will be enrolled and randomized in 1:1 ratio to receive CD24Fc or placebo. All subjects will be treated with the best available treatment. The follow up period is 28 days. Those who uses immune modulators such as IL-6/IL-6R antagonists or experimental antiviral drugs are allowed to participate the trial.

Phase III study consists of screening period and treatment/follow up period. Each subject should have 6 visits. Visit 1 (D-3 to D-1); Visit 2 (D1); Visit 3 (D4); Visit 4 (D8±1d); Visit 5 (D15±2d), Visit 6 (D29±4d).

If the patient's clinical status improves and is discharged to home care, the follow up visits can be carried out through telemedicine (phone or video interviews). The clinical investigators should make best efforts to obtain the vital signs, clinical status evaluation, concomitant medicines and adverse events assessment. The laboratory tests, radiology study, ECG and research samples are optional if the patient is discharged.

3.2. Sample size

In Phase III study, a total of 270 subjects will be enrolled in 1:1 ratio for study drug arm and placebo arm (135 subjects per arm). For the calculation method of sample size, please refer to Section 10.1.

4. ELIGIBILITY CRITERIA

4.1. Inclusion criteria

- 1) Should be at least 18 years of age,
- 2) Male or female, female should have negative pregnancy test,
- 3) Diagnosed with COVID-19 and confirmed SARS-CoV-2 viral infection, prior positive viral results allowed,
- 4) Informed consent form signed by patient or by a legally authorized representative,
- 5) Hospitalized and requiring oxygen support, NIAID 8-point ordinal score 2, 3, 4, regardless of ARDS (Appendix A), intubation for invasive mechanical ventilation should be within 7 days,
- 6) Women of childbearing potential, under the age of 54 years, who use adequate contraception and who agree to use adequate contraception for the duration of the study.

4.2. Exclusion criteria:

- 1) Patients who are pregnant, breastfeeding, or have a positive pregnancy test result before enrollment,
- 2) Patients previously enrolled in the CD24Fc study,
- 3) Intubation for invasive mechanical ventilation is over 7 days,
- 4) Documented acute renal or hepatic failure,
- 5) The investigator believes that participating in the trial is not in the best interests of the patient, or the investigator considers unsuitable for enrollment (such as unpredictable risks or subject compliance issues).

5. REMOVAL FROM STUDY

Patients have the right to withdraw from the study at any time for any reason. The clinical site PI also has the right to withdraw patients from the study in the event of intercurrent illness, adverse events, treatment failure, protocol violation, or other reasons. Should a patient (or a patient's legally authorized guardian or representative) decide to withdraw, all efforts will be made to complete and report the observations as thoroughly as possible. A complete final evaluation should be made at the time of the patient's withdrawal with an explanation of why the patient is withdrawing and every effort should be made to perform follow-up evaluations. Patients may be removed from the study treatment if one or more of the following events occur:

- Significant protocol violation or noncompliance, either on the part of the patient or the clinical site PI.
- Refusal of the patient to continue treatment and / or observations.
- Unacceptable or dose-limiting toxicity.
- Decision by the clinical site PI that removal from the study is in the patient's medical interest.
- Unrelated medical illness or complication.
- Lost to follow-up.

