6.3. Study drug administration

CD24Fc will be administered intravenously on day 1 in single dose.

Arm A: 480 mg CD24Fc diluted with normal saline to 100 ml, IV infusion in 60 min.

Arm B: Normal saline 100ml, IV infusion in 60 min.

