For the primary endpoint, during the observation period, an improvement from NIAID scale 2, 3 or 4 to scale 5 or above, if sustained without a drop below 5, is considered as an event. The days from the randomization to the first time point of such improvement will be defined as time of improvement. Additional follow-up can be used to determine clinical improvement events.

Subjects who do not withdraw or do not experience improvement will be censored on the actual date of the D29 visit.

Subjects without improvement but lost to follow-up will be censored on the last date of follow-up.

Subjects with death within 28 days will be censored on D29.

Sensitivity analysis:

(1) Imbalances in age, baseline score, use of antiviral drugs such as remdesivir, or IL-6/IL-6R antagonist, or related factors that may affect the results will be investigated with sensitivity analyses and these factors will be evaluated separately in the Cox-Model to assess their potential impact on the primary efficacy endpoint.

(2) Use only data from planned visits to analyze time to improvement in the main analysis.

(3) The days from randomization to the first clinical improvement will be analyzed.

Since there are no available best supportive case (BSC) for this disease, controlling BSC use between two arms is difficult, and consequently there may be imbalance for some particular BSCs between two arms. To evaluate whether there may be some potential bias caused by such imbalance, we will evaluate the percentage of the largest and second largest BSC used in the trial if the difference of such BSC between two arms are significant. Further analyses will be performed to study whether the efficacy results are indeed caused by such differential BSC use between two arms.

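### Section 5 lets the site PI withdraw patients from the study for treatment failure or adverse events after a single infusion, and no censoring rule names them, so the plan permits outcome-related censoring of the primary endpoint

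*Combined protocol and SAP*

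**What the plan says.** Section 6.3 sets a single administration: "CD24Fc will be administered intravenously on day 1 in single dose". Section 5 then gives two different permissions.

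- **Leaving the study.** "The clinical site PI also has the right to withdraw patients from the study in the event of intercurrent illness, adverse events, treatment failure"; the sentence also covers violations of the protocol and unspecified other reasons. The available text does not define treatment failure.
- **Leaving study treatment.** "Patients may be removed from the study treatment if one or more of the following events occur". The list includes "Unacceptable or dose-limiting toxicity", which is not defined for this trial and otherwise appears only in the Phase IIa summary (1.7.2.2). The same list also holds study-level items: loss to follow-up and "Decision by the clinical site PI that removal from the study is in the patient's medical interest".

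On what happens after withdrawal, section 5 asks for a complete final evaluation and says that "every effort should be made to perform follow-up evaluations". The lead-in to that request is the case in which the patient, or the patient's representative, decides to withdraw.

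On censoring, the endpoint definition in 10.4.1 places all subjects without improvement within 28 days at the Day 29 visit. The censorship rules later in 10.4.1 give the D29 date to subjects who have not withdrawn, and add "Subjects without improvement but lost to follow-up will be censored on the last date of follow-up" and "Subjects with death within 28 days will be censored on D29". Section 10.6 repeats the loss-to-follow-up rule. None of these names a patient withdrawn by the site PI.

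**The concern.** These removal reasons suit repeated dosing. Here, once the infusion has ended, no treatment is left to stop, so a PI withdrawal acts on observation alone. Treatment failure, on any ordinary meaning, is also the opposite of the primary event.

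If such a patient is censored at last contact, the censoring is informative. A patient who was not going to improve leaves the denominator, and the Kaplan-Meier improvement rate for that arm rises. If removals differ between arms, the log-rank test shifts towards the arm with more of them. Two patients with equally poor prognosis would be handled in opposite ways: the one who dies stays in the risk set to D29, and the one withdrawn for failure does not.

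**Working it through.** The plan states no figure for this point, so the check sets the rules side by side and then sizes the effect under stated assumptions.

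**1. Which rule applies to a PI-withdrawn patient without improvement?**

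| Source | Implied censoring |
|---|---|
| 10.4.1, endpoint definition (all non-improvers) | Day 29 visit |
| 10.4.1, censorship rules (D29 for those who have not withdrawn) | Not D29, by implication |
| 10.4.1 and 10.6, loss to follow-up | Last contact |
| 10.4.1, death within 28 days | D29 |

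The rules conflict, and last contact can only be inferred. The extra analyses in 10.6 do not settle it. The first repeats last-contact censoring; the second keeps non-improvers only if they were followed to the end of the trial. Neither treats withdrawn patients as not improved.

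**2. Inputs.** From 10.1: 135 per arm, 78% recovery, control median 11 days, one-sided alpha 0.025. These fit together: 270 × 0.78 = 210.6 events, against 208 required. Assumed, because the documents are silent: the share of non-improvers removed, and when. Non-improvers per arm: 135 × 0.22 = 29.7, so 25% is about 7 patients and 50% about 15.

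**3. Effect on one arm's improvement rate.** If removal were immediate, the Day 28 rate would be 0.78 / (1 − 0.22 × share removed):
- 25%: 0.78 / 0.945 = 82.5%
- 50%: 0.78 / 0.89 = 87.6%

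With removal spread over Days 4-14, simulation gives about 82% and 86%, against a true 78%.

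**4. Effect on the log-rank test, no true effect.** Z = U/√V, with U = Σ(d₁ − d·n₁/n) and V the hypergeometric variance; reject if Z > 1.96. The apparent HR is exp(U/V), averaged on the log scale. Two simulations were run:
- A: 3,000 trials, truncated-exponential improvement times with overall median 11 days, removal on Days 4-14.
- B: 4,000 trials, improvement times among improvers exponential with rate ln2/9 truncated at 28 days, removal on Days 2-14. The overall median solves 0.78 × (1 − e^(−λt)) / 0.884 = 0.5, so t ≈ 10.9 days, close to the plan's 11.

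| Non-improvers removed, placebo / CD24Fc | A: HR, error | B: HR, error |
|---|---|---|
| 0 / 0 | error 2.9% | 1.00, 2.6% |
| 25% / 25% | – | 1.00, 2.5% |
| 50% / 50% | – | 1.00, 2.9% |
| 10% / 30% | – | 1.07, 6.8% |
| 0 / 25% | 1.08, 7.0% | 1.08, 8.0% |
| 0 / 50% | 1.18, 20.8% | 1.19, 22.5% |
| 25% / 0 | – | 0.93, 0.7% |

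Monte Carlo standard error at 2.5% with 4,000 runs is √(0.025 × 0.975 / 4000) = 0.25 percentage points, so 2.5-2.9% is nominal within noise.

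**5. Effect on power when removal shares are equal.** Assume 72% against 84% recover (mean 78%). Power falls from 58% with no removal to 53% (25% removed in each arm) or 44% (50%), and the HR from 1.36 to 1.34 or 1.30. Equal shares take out more placebo patients because placebo has more non-improvers: 135 × 0.28 × 0.25 = 9.5 against 135 × 0.16 × 0.25 = 5.4. The 58% belongs to this assumed effect and is not the design power.

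**6. Check on the remedy.** Holding removed non-improvers in the risk set to D29, as the plan does for deaths, returns the no-removal results.

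**The case against.** Four arguments on the other side carry weight.

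- **Follow-up is not simply ended.** A reader might infer that removal in a single-dose trial can only end follow-up. The text does not support that. Section 5 asks for efforts to continue follow-up evaluations, and section 8.5 allows the infusion to be slowed or stopped, so removal from treatment has a meaning while it runs. What remains is that the request is to attempt follow-up, and that its lead-in concerns withdrawal decided by the patient.
- **Dose-limiting toxicity is not a stated reason for leaving the study.** It sits in the study-treatment list. The list itself blurs the two levels, and adverse events are separately a reason for study withdrawal, but the toxicity item alone does not take anyone out of observation.
- **Last-contact censoring is not a stated rule for these patients.** If the endpoint definition in 10.4.1 governs, they are held to Day 29 and the bias in the primary analysis disappears. The conflict with the censorship rules stands.
- **The trial is double-blind.** Blinding makes deliberate imbalance unlikely, and equal removal does not inflate the error. It does not exclude imbalance: removals driven by toxicity or lack of benefit can differ by arm under a perfect blind. The simulations remove only patients who would never improve; toxicity-driven removal would also take some who would.

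**Conclusion.** The concern holds in limited form. Section 5 permits withdrawal from observation for reasons tied to outcome, and the censoring rules conflict on how such a patient is analysed. On the last-contact reading, the primary analysis is open to informative censoring that the planned sensitivity analyses do not repair.

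Neither direction nor size follows from the documents. The inflated error rates in the table need more removal in the CD24Fc arm, at shares chosen for illustration; they are not a forecast for this trial. More removal in placebo is conservative, and equal removal overstates both improvement rates and costs power.

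A reader might also infer that a toxic arm would look better on both efficacy and safety. The text does not support that. Sections 8.1.6 and 8.3 have adverse events and SAEs documented and followed, so the event prompting removal is captured. The composite of death or respiratory failure in 10.4.2 is a cumulative count over the ITT set, so events before removal count. Only later deaths, respiratory failures and adverse events could be missed; a patient removed before a first composite event, with no later data, would be counted as free of it.

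This is worth changing because the correction is cheap and a stated permission creates the problem.

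**What to change.** 1. **Section 5.** Separate stopping or not giving the infusion from leaving the study. State that treatment failure or an adverse event does not end study observation. Follow every randomized patient to D29 for NIAID score, vital status and SAEs, by telephone or chart if needed, unless consent to follow-up is withdrawn or contact is lost.
2. **Sections 10.4.1 and 10.6.** Reconcile the endpoint definition, the censorship rules and the missing-data convention. Censor at last contact only for withdrawn consent or true loss to follow-up. Keep any PI-withdrawn patient without improvement in the risk set to D29, as for deaths.
3. **Sensitivity analysis.** Add one in which all withdrawn or lost patients without improvement count as not improved to D29.

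Clinical decisions about the infusion are unchanged. The cost is a few lines in three sections and a few extra telephone or chart contacts; the telemedicine visits already planned for discharged patients offer a route for many of them.

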6. STUDY DRUG

6.1. Study drug CD24Fc

Name	CD24Fc for IV infusion.
Vial content	120mg/12mL
Formulation	Liquid formulation for IV infusion.
Route	IV Infusion
Storage	-20°C, avoid light.
Manufacturer	Catalent, Inc.
Provider	OncoImmune, Inc

6.2. Placebo

The placebo is 0.9% Sodium Chloride Solution for IV infusion.

6.3. Study drug administration

CD24Fc will be administered intravenously on day 1 in single dose.

Arm A: 480 mg CD24Fc diluted with normal saline to 100 ml, IV infusion in 60 min.

Arm B: Normal saline 100ml, IV infusion in 60 min.

6.4. Best available treatment

The best available treatment and supportive care will be given to all subjects according to local institutional guideline. Those who uses immune modulators such as IL-6/IL-6R antagonists or experimental antiviral drugs such as remdesivir are allowed to participate the trial.

7. STUDY PROCEDURES

7.1. Procedure and tests description

7.1.1. Informed consent

The researchers explain all the research procedures to the subjects before the screening, including information about the nature of the research, and obtain informed consent signed by the patient or by a legally authorized representative.

Before the process to obtain informed consent from the legal authorized representative, investigators should use the **EVALUATION TO SIGN A CONSENT FORM FOR RESEARCH** in [Appendix B](#) to assess the understanding of the consent process of person who may have cognitive impairments, or may elicit the information using clinical interview procedures.

7.1.2. Collect demographic data

Obtain the demographic data of the subjects during the screening period, including information such as date of birth, height, weight, gender, ethnicity, and race.

7.1.3. Allergy history / medical history, previous / combined medication collection

Obtain subjects' past medical history, especially chronic diseases (such as chronic obstructive pulmonary disease, angina pectoris, hypertension, cerebral thrombosis, diabetes, etc.) during the screening period and other major diseases and drug treatment history, surgery history, allergy history, and comorbidities judged by the investigator.

It is important to obtain the number of days of onset of the symptoms, the history of exposure to confirmed cases within 14 days before the onset of the symptoms, recent temperature, and the treatment status (antiviral drugs, antibacterial drugs, oxygen therapy, duration of treatment, etc.).

Concomitant medications: from the beginning of the screening period to the end of the treatment / follow-up observation period.

7.1.4. Vital signs and physical examination

Vital signs include body temperature (° C), blood pressure (mmHg), heart rate (beats / min), respiratory rate (beats / min), which need to be performed at each visit.

On the D1 for treatment, vital signs for body temperature, blood pressure, heart rate, respiratory rate should be recorded before (0 min) and after IV infusion (60 min). The data from monitor are allowed. During the IV infusion, the data from the remote monitoring can be recorded without entering the room at 60±10 min after the start of infusion.

Physical examination will be performed during the screening period. Any changes should be recorded at D15. Check the general body surface, skin, head and neck, chest (heart, lung, breast), abdomen (gastrointestinal and liver), musculoskeletal, nervous system including taste and smell changes, lymph nodes, etc.

If the patient clinical status improves and is discharged to home care, the follow up visits can be carried out through telemedicine (phone or video interviews). The clinical investigators should make best effort to obtain the vital signs, clinical status evaluation, concomitant medicines and adverse events assessment. The laboratory tests, radiology study and research samples are optional.

7.1.5. Laboratory tests

Blood tests: red blood cell count (RBC), hemoglobin concentration (HGB), white blood cell count (WBC), platelet count (PLT), neutrophil count (ANC), lymphocyte count (LY), monocyte count (MO), Eosinophil count (EO), basophil count (BA).

Blood biochemical tests: aspartate aminotransferase (AST), alanine aminotransferase (ALT), alkaline phosphatase (ALP), γ -glutamyl transpeptidase (γ -GT), albumin (ALB), total bilirubin (TBIL), direct bilirubin (DBIL), lactate dehydrogenase (LDH), urea nitrogen (BUN) / urea (Urea), creatinine (Cr), creatine kinase (CK), creatine kinase isoenzyme (CK -MB), fasting blood glucose and cardiac Troponin I.

C-reactive protein (CRP), ESR.

Urine routine examination: urine pH, urine red blood cells, urine white blood cells, urine protein, urine glucose, urine ketone body.

Examination of coagulation function: D-dimer, prothrombin time (PT), activated partial thromboplastin time (aPTT), thrombin time (TT), plasma fibrinogen (Fbg).

Laboratory tests should include CBC, blood biochemistry, CRP, coagulation function and urine test during the screening period and the treatment / follow-up observation period (D1, D4, D8 and D15).

Laboratory tests done at Day 1 should be done prior to the infusion.

If the patient clinical status improves and is discharged to home care, the follow up visits can be carried out through telemedicine (phone or video interviews). The laboratory tests, radiology study, ECG and research samples are optional.

